10.3 Columbia Suicide Severity Rating Scale (C-SSRS)

The C-SSRS is an instrument that measures suicidal ideation and behavior. Items measuring suicidal ideation and suicidal behavior are displayed in the table below. Frequency counts of yes/no responses to items below and whether any suicidal ideation or behavior is present will be summarized as described below.

The overall number of participants with any suicidal ideation or behavior (by type and in total) or self-injurious behavior while on-treatment will be provided by treatment group. For ideation, participants will only be counted once at each visit and/or time frame at the worst-case response for ideation type (1-5), where 1 is the least severe and 5 is the most severe type of ideation.

Category	Items
A) Suicidal	(1) Type 1: Wish to be dead
Ideation	(2) Type 2: Non-specific active suicidal thoughts
	(3) Type 3: Active suicidal ideation with any methods (not plan)
	without intent to act
	(4) Type 4: Active suicidal ideation with any some intent to act,
	without specific plan
	(5) Type 5: Active suicidal ideation with specific plan and intent
B) Suicidal	(1) Preparatory acts or behavior
Sehavior	(2) Aborted attempt
	(3) Interrupted attempt
	(4) Actual attempt
	(5) Completed suicide
	Suicidal Behavior present (composite of items 1-5)
	Non-Suicidal Self-Injurious Behavior

Suicidal intensity of ideation will be calculated by tallying up the five intensity items to create a total score ranging 0-25. If a participant does not have any suicidal ideation, a score of 0 will be given. Separate tables will be created for the entire Safety Population

Protocol: TNX-CY-P306 Page 23 of 36

Final v1.0

as well as the population comprising only participants exhibiting any suicidal ideation. Suicidal intensity of ideation total score will be summarized using descriptive statistics by treatment group.

A data listing of C-SSRS results will include only participants with suicidal ideation, suicidal behavior, or self-injurious behavior without suicidal intent. For participants with suicidal ideation, suicidal behavior, or self-injurious behavior without suicidal intent at any time, data from all visits are displayed.

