#### **Safety Analyses:**

Safety data will be summarized as a single treatment group receiving 1 or more doses of TNX-102 SL 5.6 mg. Adverse events will be coded using the same version of the Medical Dictionary for Regulatory Activities (MedDRA) as used for the lead-in HONOR study and will be summarized overall and by preferred term and system organ class (SOC). Adverse events will also be summarized by severity and relationship to study drug. Serious AEs and AEs leading to discontinuation of study drug will also be summarized. Adverse events that are ongoing in the 12-week open-label extension study P303 or the lead-in double blind HONOR study will be transcribed into the eCRF. All other adverse events that are reported after starting TNX-102 SL in this extension study, or that worsen after entry into this extension study, will be considered newly emergent AEs (NEAEs), even if the type of event was previously reported (and resolved) during either the HONOR study or the 12-week open-label extension study.

Actual values and change from baseline for clinical laboratory test results, vital sign measurements, depression status via the BDI-II and PTSD symptom status via the PCL-S, will be summarized at endpoint using descriptive statistics (n, mean, SD, median, minimum, and maximum). The number of

<sup>1 Tonmya is the FDA conditionally accepted proposed proprietary name for TNX-102 SL for the treatment of PTSD.

patients with baseline and treatment-emergent suicidal ideation and/or suicidal behavior or self-injurious behavior, based on the C-SSRS, will be summarized by treatment group.

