## 6.3. Study Endpoints

## **6.3.1.** Safety

Safety will be assessed by:

- Adverse events (AEs) and serious AEs (SAEs) throughout the entire duration of the study, including assessment of AEs involving the oral cavity
- Change from baseline in clinical laboratory test results
- Changes from baseline indicative of increased suicidal ideation or behavior as assessed by the Columbia Suicide Severity Rating Scale (C-SSRS)
- Change from baseline in Beck Depression Inventory-II (BDI-II)
- Changes from baseline in vital signs and weight
- Track A patients only: Change from Visit 5 to Visit 6 in PTSD Checklist-Specific Version (PCL-S)
- Track B patients only: Change from Visit 5 to Visit 7 in PTSD Checklist-Specific Version (PCL-S)

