# 12.1. Evaluation of Safety

Safety data will be summarized as a single treatment group receiving 1 or more doses of TNX-102 SL (patients that have taken only 1 tablet of TNX-102 SL will be included).

Safety will be assessed by the monitoring and recording of AEs, clinical laboratory tests, vital signs, visual examination of the oral cavity findings, the monitoring of suicidality using the Columbia C-SSRS scale, and patient-rated assessments of depressive symptomology (BDI-II) and PTSD symptomology (PCL-S).

AEs will be coded using the MedDRA and will be summarized overall and by preferred term and SOC. AEs will also be summarized by severity and relationship to study drug. SAEs and AEs leading to discontinuation of study drug will also be summarized.

Actual values and changes from the extension study baseline values for clinical laboratory test results and vital sign measurements will be summarized at endpoint using descriptive statistics (n, mean, standard deviation (SD), median, minimum, and maximum). Laboratory values will be displayed in the data listings along with corresponding normal ranges, and those that are outside the normal range will be flagged.

Based on the C-SSRS results, the frequency and severity of suicidal ideation and behavior will be tabulated at each time point. The number of patients with baseline and treatment-emergent suicidal ideation and/or suicidal behavior or self-injurious behavior, based on the C-SSRS, will be summarized by treatment group.

All data gathered will be listed by patient and parameter, and clinically significant abnormalities should be recorded as AEs. AEs of special interest indicating potential abuse and dependency will be evaluated and summarized as described in the Statistical Analysis Plan.

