2.2.2 Safety Endpoints

Safety will be assessed by:

- Adverse events (AE) and serious AEs (SAEs) throughout the entire duration of the study, including detailed assessment of AEs involving the oral cavity.
- Changes from baseline in clinical laboratory test results.
- Changes from baseline in vital signs and weight.
- Change from baseline in BDI-II.
- Suicidal ideation or behavior as reported on the Columbia-Suicide Severity Rating Scale (C-SSRS).

Protocol: TNX-CY-P306 Page 10 of 36

Final v1.0

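### SAP 10.3 counts any on-treatment suicidality and plans no table of the treatment-emergent number that the protocol requires; SAP 13 does not declare the change

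*SAP*

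**What the plan says.** **Protocol.** Section 6.3.1 lists as a safety endpoint "Changes from baseline indicative of increased suicidal ideation or behavior as assessed by the Columbia Suicide Severity Rating Scale (C-SSRS". Section 12.1 then sets two analyses. The first is by visit: "the frequency and severity of suicidal ideation and behavior will be tabulated at each time point". The second, which is to be split by treatment group, is by patient: "The number of patients with baseline and treatment-emergent suicidal ideation and/or suicidal behavior or self-injurious behavior, based on the C-SSRS, will be summarized". The Safety Analyses part of the synopsis repeats the second requirement.

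**SAP.** Section 2.2.2 shortens the endpoint to "Suicidal ideation or behavior as reported on the Columbia-Suicide Severity Rating Scale (C-SSRS", without the reference to change or increase. Section 10.3 plans a count of everyone "with any suicidal ideation or behavior (by type and in total) or self-injurious behavior while on-treatment will be provided by treatment group". Treatment group here means the arm randomised in the lead-in study (SAP 3.2); everyone takes TNX-102 SL in P306. Ideation is graded by type, 5 being the most severe, and the counting rule is that "participants will only be counted once at each visit and/or time frame at the worst-case response for ideation type (1-5". The section also plans descriptive statistics of a 0–25 intensity score and a listing.

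SAP 10.3 contains no definition of treatment-emergent, no rule for new onset or worsening, and no shift table. SAP 12, the long-term safety section, has no C-SSRS analysis. SAP 13 declares one departure from the protocol, the renumbering of Day 0 as Day 1.

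**The concern.** The primary objective is long-term safety, and suicidality is a named safety endpoint in a PTSD population. The protocol's question is whether ideation or behaviour appeared or worsened relative to the patient's own starting point. The SAP's count answers a different question: how many patients had any ideation or behaviour while on drug. A patient with the same mild ideation at every visit and a patient who develops ideation for the first time both add one to it.

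P306 has no untreated arm, so the patient's own baseline is the main reference for reading these data. If the SAP is followed as written, the study report will lack a safety result that the protocol promises twice, and SAP 13 will not tell the reader that it was dropped.

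**Working it through.** The plan states no figure on this point, so there is nothing to reproduce. The check compares the texts and then asks what the planned counts can identify.

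**1. Is there a protocol requirement that no SAP table meets?**
- Frequency and severity at each time point (Protocol 12.1): met by the SAP's counts at each visit by worst ideation type.
- Number of patients with baseline suicidality (Protocol synopsis and 12.1): not named in SAP 10.3. SAP 8.3 says generally that baseline values appear alongside follow-up values, so it is probably displayed.
- Number with treatment-emergent suicidality (same places): not defined and not tabulated.
- Change from baseline indicating an increase (Protocol 6.3.1): no patient-level rule in the SAP.

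**2. Does the SAP avoid baseline contrasts as a policy?** No. SAP 10.1 defines newly emergent adverse events. SAP 10.2 plans laboratory shift tables from baseline. SAP 12.3 counts a vital sign as treatment-emergent only if the abnormality was absent at baseline. SAP 12.4 plans treatment-emergent laboratory shifts. The C-SSRS, where the protocol asks for the contrast by name, has none. This looks like an omission.

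**3. Can ideation be present at the P306 baseline?** Yes. Inclusion criterion 4 (Protocol 7.2) is aimed at a clinically important rise in ideation, with plan or intent, during the earlier studies. It does not exclude stable, milder ideation.

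**4. Do the baseline and on-treatment counts together give the emergent number?** Let N be the number of patients, b the number positive at baseline, and k the number positive on treatment. The number of new-onset cases then lies between max(0, k − b) and min(k, N − b).

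Take N = 200, the maximum enrolment in the protocol, and k = 20. The values of k and b are assumptions, chosen only to show the width of the interval.
- b = 0: max(0, 20) = 20 and min(20, 200) = 20, so exactly 20.
- b = 10: max(0, 10) = 10 and min(20, 190) = 20, so 10 to 20.
- b = 20: max(0, 0) = 0 and min(20, 180) = 20, so 0 to 20 (0% to 10% of 200).
- b = 30: max(0, −10) = 0 and min(20, 170) = 20, so 0 to 20.

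Unless b = 0, the two counts do not fix the emergent number, even printed side by side. These bounds cover new onset only. Worsening among patients already positive is a further unknown: one patient moving from type 1 to type 3 while another moves from 3 to 1 leaves the by-type counts unchanged. A patient-level cross-classification is needed.

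**5. Is the baseline itself clear?** Only partly. SAP 7.1 takes the latest available value before the first P306 dose. Protocol 9.1.2 uses either the P303 final visit or P306 Visit 1. The Methodology part of the synopsis also allows Track A patients' final HONOR-visit safety values. Protocol 10.4.1.1 uses the since-last-visit form at all study visits, so the baseline recall period depends on when the preceding visit took place.

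**The case against.** The strongest reply is that the information is largely there already.

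- **Group-level display.** SAP 7.1 summarises by visit, SAP 8.3 shows baseline values with follow-up, and SAP 10 allows change from baseline for continuous measures where appropriate, which could cover the intensity score. A group trend from baseline would be visible.
- **Listing.** SAP 10.3 lists every visit for any participant with a positive finding, so emergent cases can be found by hand.
- **Adverse events.** A significant C-SSRS change towards higher risk is to be recorded as an AE (Protocol 10.4.1.1), and an ideation score of 4 or 5 leads to an SAE report (Protocol 10.4.1.2). SAP 10.1 and 10.1.2 tabulate newly emergent AEs and SAEs, and suicidal ideation is a preferred term in SAP Appendix 3.
- **Scope.** With a since-last-visit form, behaviour or self-injury reported after baseline is essentially an event of that interval. Types 4 and 5 are unlikely to be carry-over, given inclusion criterion 4.

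All of this stands, and it narrows the point. A reader might infer that the SAP cannot show any increase in suicidality, or leaves the study with no internal reference. The documents do not support that, because the routes above exist.

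They still do not supply the missing result. Group trends do not identify patients who changed. A listing without a definition leaves each reader to invent one. AE capture depends on the site judging a change significant. The lead-in-arm split gives no untreated reference. What remains is mainly the mixing of persisting and new or worsened lower-grade ideation (types 1 to 3).

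A fair caution also applies to the remedy. A shift table compares one baseline assessment with the worst of several later ones, which favours apparent worsening. The schedule gives four on-treatment clinic assessments in Track A (Weeks 7, 16, 28, 40) and five in Track B (adding Week 52), plus the Week 2 call for patients entering from P301. Some patients are also already on TNX-102 SL at the P306 baseline.

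**Conclusion.** The point holds in a limited form. The protocol requires baseline and treatment-emergent C-SSRS counts and an endpoint of change towards increase. SAP 10.3 replaces these with any on-treatment counts, no planned summary gives the emergent number, and SAP 13 does not declare the change. The text comparison alone supports this conclusion; it needs no assumed rates.

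The size is one protocol-specified safety summary missing and only partly recoverable from other outputs. No hypothesis test is affected. The documents contain no baseline or on-treatment C-SSRS frequencies, so any percentage for the distortion would be invented. The interval of 0 to 20 in 200 shows only that the planned counts do not identify the quantity; it is not an estimate.

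**What to change.** In SAP 10.3:

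1. Define treatment-emergent ideation as new ideation, or a worst on-treatment type higher than at the P306 baseline. Define treatment-emergent behaviour and self-injury separately.
2. State which assessment is the C-SSRS baseline (P303 final visit or P306 Visit 1) and what recall period it covers under the since-last-visit form. Reconcile this with the synopsis wording on final HONOR-visit values.
3. Tabulate baseline and emergent counts, with a shift table of baseline category (none, types 1 to 5) by worst on-treatment category, pooled and by lead-in arm.
4. Keep the existing on-treatment counts, intensity summaries and listing.
5. Add a table note that one baseline assessment is compared with the worst of several, which tends to favour apparent worsening, and that emergent means emergent in P306 because some patients were already taking TNX-102 SL.

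Restore the change-from-baseline wording in SAP 2.2.2. If the sponsor prefers not to produce these counts, SAP 13 should declare and justify the departure.

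The cost is a short definition and one additional table from data already collected. No visit or assessment changes.

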10.4 Vital Signs

Descriptive summaries (mean, SD, median, minimum, and maximum) of actual values and change from baseline at each assessment time point and last on-treatment assessment will be calculated for vital signs including weight, BMI, body temperature, pulse rate, systolic blood pressure and diastolic blood pressure. 95% confidence intervals will be presented for change from baseline.

These summaries will be presented by assessment time for the Safety Population. ET data will be analyzed with the closest visit that does not have a valid assessment value.

10.5 Visual Examination of Oral Cavity

A visual examination of the oral cavity will be assessed at Baseline and Week 12. A visual examination is to be done any time a participant spontaneously reports an oral adverse event (aside from AEs known to be sensory-only, such as numbness, tingling or bitter taste) to confirm presence or absence of any signs of irritation or other visible abnormalities. A data listing of the visual examination results performed at each scheduled visit and at the time of an adverse event will be presented.

11. MEDICATIONS

11.1 Concomitant Medication

All medications will be coded using the World Health Organization Drug Dictionary (WHO-DD) Version September 2016. Prior and concomitant medications will be summarized by treatment group and by the number and percentage of participants taking each medication, classified by using WHO-DD Anatomical Therapeutic Chemical Level 3 and preferred term.

Prior medications are defined as medications or therapies initiated prior to the start of the study drug and terminating prior to the start of study drug in protocol P301. Hence, these medications or therapies will have end dates prior to the first dose date of study drug. Concomitant medications are defined as any medications other than the study drug that a participant receives concurrently with the study drug. These medications will have end dates on or after the first dose date of the study drug until ten days after last dose date.

There should be no new prior medications recorded in protocol P306 as these should be captured entirely in P301. Concomitant medications will be summarized ATC Level 3 and preferred name. All medications will be presented in a listing.

Please refer to Section 7.3 for the conventions used to impute partial start dates and end dates of concomitant medications.

Protocol: TNX-CY-P306 Page 24 of 36

Final v1.0

11.2 Exposure and Compliance

The treatment duration will be calculated as (number of days=last dose date — first dose date+1) and summarized. Participants that are lost to follow up or have a missing last dose date will be assigned a last dose date of the day before the last attended clinic visit for analysis purposes.

All pill count shortage (negative pill count) of greater than 4 doses (8 tablets) per 4-week assessment period and/or any between-visit compliance <70% will be considered protocol deviations, and the reason for the pill count discrepancy will be discussed with the participant and documented in the CRF to ensure that any cases of potential abuse or misuse are identified. Participants with more than one significant incidence of negative pill count discrepancy during the double-blind phase of the study will be closely monitored by the investigator.

Exposure in P306 will be measured using the last date of treatment and first date of treatment. Total exposure will be defined as the last date of treatment minus the first date of treatment plus one. The number of participants with total exposure by visit weeks (eg, 0-12 weeks, >=12-24 weeks, >=24-36 weeks, >=36-48 weeks, and >=48 weeks) will be presented. Additionally, exposure days, defined as the total number of tablets taken divided by 2 (and rounded up to the nearest whole number), will be summarized.

Compliance will similarly be summarized across all study visits for each treatment arm. Study drug compliance as a percentage will be defined as the number of pills taken by the participant divided by the total number of pills that the participant was assigned to take multiplied by 100.

For calculating the compliance and exposure days, the following convention will be applied: for periods where drug is issued, but the participant does not return any bottles or tablets, or the participant misses the visit entirely, that period will not contribute to the compliance or exposure calculation unless the bottles are returned at a later visit.

Compliance will be summarized with descriptive statistics by treatment arm. The number and percentages of participants within certain categories of compliance e.g. <50%, 50% to <70%, 70% to <100%, >100% will be presented. Compliance between 70% to 114% will not be considered a protocol deviation. Tablet counts, calculation of compliance overall and by visit, and participant-reported reasons for all tablet discrepancies at all visits will be presented in a listing.

In addition, participants with significant over-usage or otherwise unaccounted-for missing tablets resulting in >114% compliance for any visit (e.g., failure to return >8 tablets per 4 week interval) will be summarized by visit and overall. These listings will include both the participant-reported reason for the discrepancy plus the investigator's assessment of potential abuse, misuse or diversion. Clinically significant drug accountability discrepancies associated with missing medication, loss of drug, or cases in which the PI confirms concern over drug abuse, misuse or diversion, will be examined and discussed in the CSR.

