## 9.2. Visit 2 (Telephone Visit: Week 2)

For patients enrolled from the double-blind lead-in study, P301/HONOR only: Visit 2 will be done as a telephone call to the patient and should be conducted after 2 weeks of treatment, on Day  $14 \pm 3$  days.

The following steps should be completed:

- Assess changes in concomitant medications
- Assess study drug compliance based on patient verbal report
- Assess occurrence of AEs, including any oral AEs and whether an unscheduled visit is indicated for an examination of the oral cavity
- Review patient instructions regarding drug dosing and storage
- Administer the 'Since Last Visit' C-SSRS telephonically

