6. ANALYSIS POPULATIONS

The following analysis populations are planned for this study:

• Safety Population (SAFETY): All participants who receive at least 1 dose of study drug in Study TNX-CY-P306. Participants who are issued study drug, but return 100% of it (i.e., none consumed) will be excluded from the Safety Population; likewise, participants that have no follow up following receipt of study drug to indicate they took drug are excluded. All analyses will be performed using this population, unless otherwise specified in this SAP.

Protocol: TNX-CY-P306 Page 14 of 36

Final v1.0

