In addition, the incidence of patients with each category of oral cavity TEAEs will be summarized by increments based on the relative start day of the AE compared to first dose of active drug in any study (0-12 weeks, >12-24 weeks, >24-36 weeks, >36-48 weeks, and >48 weeks). Intervals may be changed for more meaningful interpretation based on the actual distribution of the AE data. For each increment, the denominator will be the number of subjects with risk-time extending into that time interval, specifically, with a duration of exposure to TNX-102 SL of at least the lower limit of that increment. For instance, the number of subjects with >12 weeks of exposure would be the denominator for the >12-24 week increment. Duration of exposure is defined in Section 12.5). The last dose date is the last dose date in Study TNX-CY-P306, and the first dose date is the first dose of TNX-102 SL in any study. If a subject experienced more than one TEAE in a given category, the first event will be selected.

A similar analysis will be provided for the incidence of TEAEs and serious TEAEs by SOC and preferred term.

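### The SAP 11.2 last-dose rule gives 0 days of P306 exposure, with last dose before first dose, to a direct P301 entrant who confirms dosing at the Week 2 call and is lost before Week 7

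*SAP*

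**What the plan says.** SAP 11.2 defines duration by dates: "The treatment duration will be calculated as (number of days=last dose date — first dose date+1) and summarized". It repeats the formula for P306 exposure: "Total exposure will be defined as the last date of treatment minus the first date of treatment plus one".

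For incomplete cases it says "Participants that are lost to follow up or have a missing last dose date will be assigned a last dose date of the day before"; its anchor is "the day before the last attended clinic visit for analysis purposes". The two conditions are joined by *or*, so the rule covers every participant lost to follow-up, including one whose last dose date is recorded. There is no exception for telephone contact and no minimum duration.

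Protocol 9.2 gives patients entering directly from P301 a telephone visit on Day 14 ± 3, with the instruction "Assess study drug compliance based on patient verbal report". Adverse events, medication changes and the C-SSRS are also covered in that call. Protocol 9.1.5 starts dosing on the evening of Visit 1, and Protocol 9.3 puts the next clinic visit at Week 7.

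On the analysis set, SAP 6 says that "participants that have no follow up following receipt of study drug to indicate they took drug are excluded". In the long-term analyses, SAP 12.2 says "The last dose date is the last dose date in Study TNX-CY-P306".

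**The concern.** The rule works once a patient has attended a clinic visit after baseline. Before that, the only clinic visit is the day of the first dose, and going back one day from it puts the last dose before the first. Direct P301 entrants are the group for whom the protocol schedules evidence of dosing in that gap, through the Week 2 call, and the rule ignores that evidence.

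Long-term safety is the primary objective, so exposure is a core output. The plan would report zero exposure for a patient known to have dosed, and the analysis datasets would hold an impossible date order. Any other derivation that uses the last dose date could inherit the error.

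**Working it through.** The plan states no exposure figure to reproduce, so the check is date arithmetic on its formula.

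**Inputs**
- First dose: evening of Visit 1, date D (Protocol 9.1.5).
- Visit 1 is an in-clinic visit, and the Week 2 contact is listed separately as a telephone visit (Protocol 6.1; SAP 3).
- Telephone visit: D + 14, window D + 11 to D + 17 (Protocol 9.2).
- Duration = last dose − first dose + 1 (SAP 11.2).

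**Control case.** For a patient last seen in clinic on Day 49, the assigned last dose is D + 48 and duration is 48 + 1 = 49 days. Last clinic days 112, 196, 280 and 365 likewise give 112, 196, 280 and 365. The rule behaves properly here.

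**Lost between the call and Week 7.** The last clinic visit is D and the assigned last dose is D − 1. Duration = (D − 1) − D + 1 = **0 days**. If the first dose was actually taken the day after Visit 1, the result is −1.

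**What the call supports.** With the same day-before convention applied to the call, a Day 14 call gives 13 + 1 = 14 days, and the window gives 11 to 17. If the call date itself is used, the result is 15 (12 to 18).

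**Does anything else correct it?**
- SAP 6 removes only patients with no follow-up showing that drug was taken. This patient has such follow-up and stays in.
- Tablet-based exposure days (SAP 11.2) omit a dispensing period from which nothing is returned, so the first period contributes nothing.

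**Where the date goes next**
- *Summary statistics.* Each such patient sets the minimum to 0. With 200 patients, the enrolment ceiling, each lowers the overall mean by 14/200 = 0.07 days (11/200 = 0.055 to 17/200 = 0.085).
- *Concomitant medications.* The window in SAP 11.1 ends ten days after the last dose: (D − 1) + 10 = D + 9. The earliest call is D + 11, so the window closes before it. A medication with no stop date is still counted as concomitant under SAP 7.3.1.
- *Long-term increments (SAP 12.2), if the same date is carried over.* Events are placed by start day from the first active dose, and denominators by duration of exposure. Let E be the days from first active dose in P301 to the day before P306 Visit 1. Assigned duration is E. Duration supported by a Day 14 call is E + 14. The >12-week (84-day) denominator differs only if E ≤ 84 and E + 14 > 84, that is E from 71 to 84 (74 to 84 for a Day 11 call, 68 to 84 for a Day 17 call).
- *Example.* Take E = 77 (11 weeks) and an event starting on the tenth day of P306 dosing. The event falls on day 77 + 10 = 87, in the >12–24 week increment. Assigned exposure is 77 days, so the patient is not in that denominator. The call supports 77 + 14 = 91 days, which would include the patient.

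**The case against.** The strongest reply is that this is a rare edge case in a descriptive table. Anchoring on an attended clinic visit is reproducible and conservative, and a verbal report is weaker evidence than a tablet count. For a P301-placebo patient, 0 days and 11–17 days fall in the same 0–12 week category and the same first-increment denominator. SAP 12 also warns that its definitions may differ, and neither 12.2 nor 12.5 cites the rule in 11.2, so carry-over is not stated. All of this stands and keeps the point minor. It does not justify a last dose earlier than the first.

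A reader might infer more than the documents support:
- **Suicidal ideation reported at the call would be dropped.** SAP 10.3 says counts of ideation, suicidal behavior "or self-injurious behavior while on-treatment will be provided by treatment group", but the SAP never ties on-treatment to the last dose date. The effect arises only if the programmers do so.
- **Adverse events would be lost.** Newly emergent events (SAP 10.1) and long-term treatment-emergent events (SAP 12.2) are defined by onset after dosing starts, with no last-dose cut-off.
- **The aim of 52 weeks' exposure in at least 50 patients is at risk.** A patient lost before Week 7 of P306 could not reach 52 weeks. Prior exposure in the 12-week P301 study plus 7 weeks is at most about 19.
- **Up to 12 weeks of exposure could vanish for later losses.** Week 2 is the only scheduled call, and unscheduled visits are returns to the clinic, which the rule already counts. A larger loss needs an ad hoc contact that documents dosing, and the protocol does not require one.

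**Conclusion.** The point holds as a small but definite defect in a stated rule. A direct P301 entrant who confirms dosing at Week 2 and is lost before Week 7 receives an assigned last dose on the day before the first dose and 0 days of P306 exposure, against about 14 (11 to 17) supported by the call. If that patient had placebo in P301 and the date is carried into SAP 12.5, total TNX-102 SL exposure is also 0.

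The conclusion assumes a first dose on the evening of Visit 1, no unscheduled or early termination clinic visit, no later bottle return, and that clinic visit excludes the telephone visit, as both documents consistently treat it. The documents do not give the number of such patients, which could be zero. The long-term denominator mismatch needs two further conditions: carry-over of the date into Section 12, and a P301-active entrant close to 12 weeks of cumulative exposure.

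**What to change.** Amend SAP 11.2 so that:
1. A recorded last dose date is used whenever there is one, including for participants lost to follow-up.
2. Otherwise the last dose date is the later of (a) the day before the last attended clinic visit and (b) the latest date on which dosing is documented, including the Week 2 telephone visit.
3. The date is never earlier than the first dose date.
4. The same date is used in SAP 12.2 and 12.5.

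Say also whether a call at which dosing is confirmed supports dosing to the day before (14 days for a Day 14 call) or to the call date (15 days). The day before matches the present convention and bedtime dosing.

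The cost is a short SAP edit and a minor change to one date derivation. The downside is some reliance on verbal report. Protocol 9.2 asks for compliance by verbal report, not for a dated last dose, so the team should check what the CRF captures before settling the wording. If nothing usable is recorded, the floor in item 3 still removes the impossible date order.
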